CGT	Card Guessing Task
CIWA	Clinical Institute Withdrawal Assessment
CMP	Complete Metabolic Panel
C-SSRS	Columbia -Suicide Severity Rating Scale
CR	Cue Reactivity
CRF	Case Report Form
CT	Computed Tomography
DBS	Deep Brain Stimulation
DD	Delay Discounting
DDD	Drinks per Drinking Day
DHHS	Department of Health and Human Services
DSMB	Data Safety Monitoring Board
DSM-V	Diagnostic and Statistical Manual of Mental Disorders, 5 th Edition
ECG/EKG	Electrocardiogram
EEG	Electroencephalogram
EHR	Electronic Health Record
FDA	Food and Drug Administration
FDG	Fluorodeoxyglucose
GABA	Gamma-aminobutyric acid
GCP	Good Clinical Practice
GGT	Gamma-glutamyl transferase
HARS	Hamilton Anxiety Rating Scale
HIPAA	Health Insurance Portability and Accountability Act
ICH	International Conference on Harmonisation
IDE	Investigational Device Exemption
INR	International Normalized Ratio
IRB	Institutional Review Board
ITT	Intention-To-Treat
LP	Limbic Pallidum

MADRAS	Montgomery Asberg Depression Rating Scale
Mini-MASQ	Mood and Anxiety Sympton Questionnaire
MPI	Multiple Principal Investigator
MRI	Magnetic Resonance Imaging
NCT	National Clinical Trial
NIH	National Institutes of Health
OCDS	Obsessive Compulsive Drinking Scale
PD	Parkinson's Disease
PDA	Percent Days Abstinent
PET	Positron Emission Tomography
PEth	Phosphatidylethanol
PI	Principal Investigator
PSQI	Pittsburgh Sleep Quality Index
PT	Prothrombin Time
aPTT	activated Partial Thromboplastin Time
RBANS	Repeatable Battery for the Assessment of Neuropsychological Status
SAE	Serious Adverse Event
SCID-R	Structured Clinical Interview for the DSM-V for Research
SSRT	Stop Signal Reaction Time Task
SUD	Substance Use Disorder
TLFB	Timeline Followback
UPMC	University of Pittsburgh Medical Center
UPPS-P	Urgency, Premeditation, Perserverance, Sensation seeking, Positive urgency, Impulsive Behavior Scale
WASI	Wechsler Abbreviated Scale of Intelligence
WHODAS 2.0	World Health Organization Disability Assessment Schedule 2.0
WTAR	Wechsler Test of Adult Reading
YMRS	Youth Mania Rating Scale

1 Protocol Overview

Study Description	This is a pilot open label clinical study to test the safety, tolerability and feasibility of Deep Brain Stimulation (DBS) of the limbic pallidum in patients with severe Alcohol Use Disorder (AUD). Participants with severe AUD will undergo baseline medical and psychiatric assessments, cognitive and behavioral testing, and positron emission tomography (PET) imaging. One to two weeks later, participants will undergo neurosurgical implantation of DBS electrodes in the limbic pallidum and a neurostimulator. Four weeks after DBS system implantation, the DBS system will be turned ON and the stimulation parameters optimized. Participants will be followed biweekly then monthly, and will then undergo repeat comprehensive assessment after 6 and 12 months of DBS stimulation.
Study Population:	3 participants of all genders, 21-75 years old, with severe AUD and advanced liver disease (stage 3 liver fibrosis, or compensated cirrhosis), living in Western Pennsylvania.
Planned Sample Size:	3
Participating Institutions (if a multi-center clinical trial)	This study will be conducted at the University of Pittsburgh Medical Center in Pittsburgh, PA.

1.1 Study Schema

2 Background and Rationale

Study goal: We propose to test a novel treatment approach for severe AUD: neuromodulation of the reward circuit with Deep Brain Stimulation (DBS) of the limbic pallidum.

2.1 Background

The limbic pallidum (LP) is an output nucleus of the basal ganglia with dense connections within the reward circuitry, receiving inputs from the ventral striatum and projecting to multiple limbic areas, including the limbic thalamus, limbic hypothalamus, and ventral tegmental area[1-5]. The LP encodes the hedonic value and valence, positive and negative, of environmental stimuli. It integrates the various cues and contingencies to result in adaptive behaviors that seek rewards and avoid aversive outcomes [4, 6-13]. Reward-associated cues are assigned incentive value in the pallidum, such that LP neuronal firing both predicts, and is necessary for, behavioral reward seeking in response to these cues[9, 10]. Importantly, value signals encoded by the LP both precede and are more robust than those in the ventral striatum, the site more traditionally associated with this integrative role[6, 9, 14]. The LP plays a similarly vital role in the learning of avoidance behaviors in response to aversive stimuli, such that non-selective pharmacologic or optogenetic LP activation results in impaired learning of appropriate avoidance behaviors[11-13, 15-17]. Previous studies using single-unit recordings identify two populations of neurons that preferentially respond to these two types of stimuli, with GABAergic neurons primarily firing in response to appetitive stimuli and encoding reward and motivation, and glutamatergic and parvalbumin neurons primarily responding to aversive stimuli and encoding aversion[11, 13, 18-22].

Adaptive responses to stimuli are disrupted in substance use disorders (SUD), and this is reflected in changes to the LP. Pre-clinical studies demonstrate several substance-induced neuroadaptations in the LP that likely underlie such processing dysfunctions, such as alcohol-induced biased LP neuronal firing towards reward, or cocaine-induced alterations of baseline glutamate and GABA concentrations and neuronal firing in the LP[4, 23-27]. Importantly, neuromodulation of the LP using opto- or chemo-genetics inhibits relapse to drug seeking, including alcohol, in animal models of drug addiction, *without* affecting the physiology or behavior of non-drug treated animals[19, 25, 28-31]. These studies demonstrate the LP is necessary and sufficient for relapse to drug seeking. The LP is also implicated in the manifestation of anhedonia and apathy, such that increased firing of LP parvalbumin neurons is causally related to social withdrawal and behavioral despair in mouse models of depression[21]. This parallel role of the LP is highly relevant for *alcohol use disorder* (AUD), given that it is so often comorbid with depression and anxiety[8].

Preclinical findings are further bolstered by human case studies highlighting the role of the LP in impulsivity, motivation, and relapse to drug seeking: bilateral lesions of the LP result in immediate and sustained abstinence and loss of craving in subjects with severe alcohol and opioid use disorders[32, 33]. Grossly, the pallidums of binge-drinkers are noticeably smaller, and individuals with a history of cocaine addiction demonstrate molecular changes post-mortem, compared to controls[34, 35].

DBS involves implanting electrodes into the brain to allow circuit-based neuromodulation, which normalizes function through functional lesioning. DBS is currently standard of care for treating Parkinson's disease, essential tremor, and dystonia, and is approved by FDA Humanitarian Device Exemption for further indications[36-40]. It has unique advantages in its ability to (1) selectively target the circuit of interest, while minimizing off-target effects and (2) enact clinical improvement independent of disease etiology[41-47]. Due to its efficacy and favorable safety profile, DBS has been used in pilot trials for the treatment of SUDs like alcohol and opioids[48-56]. In animal models of AUD, ventral striatal DBS inhibits

relapse to alcohol seeking and other drugs. A case report and a pilot study of five patients implanted with ventral striatum DBS in patients with AUD have been reported[57-59]. Though the sample size was small, data suggested a significant and long-lasting efficacy in reducing relapse to alcohol. Pilot DBS trials for SUDs have exclusively targeted the ventral striatum; no SUD DBS trials have targeted the LP, despite the overwhelming pre-clinical and clinical literature regarding the role of the LP in reward and motivation processing and relapse to drug seeking.

Further DBS studies demonstrate the benefit of LP modulation in non-SUD disorders of impulsivity [60-64]; LP DBS in medically refractory patients with Tourette's syndrome and Lesch-Nyhan syndrome effectively decreased compulsive behaviors[39, 65-68]. Similarly, GPi DBS with closer volume of tissue activation to the LP was more effective in decreasing impulsivity measures in PD patients[69]. In the context of SUD treatment, modulating impulsivity is vital, as impulse control problems are central to addiction behaviors, especially relapse[70-72]. Given the observed therapeutic potential of DBS in AUD patients, the clinical evidence supporting the efficacy of LP-targeted neuromodulation in impulsivity disorders, and the pre-clinical evidence supporting role of neuromodulation in inhibiting relapse to drugs, including alcohol, the present study intends to investigate the safety and feasibility of LP DBS in patients with AUD, with the ultimate goal of conducting efficacy studies in the future.

Advantages of LP DBS over ventral striatum DBS: 1) Clinical cases show that bilateral lesions of the LP in patients with AUD result in sustained and complete remission of AUD [33, 73]. No such evidence is available for other brain regions, including the VS; 2) the LP plays a unique and critical role in integrating environmental stimuli to optimize adaptive behaviors (approach of rewarding outcomes and avoidance of aversive outcomes)[18, 74], a process that is impaired in substance use disorders; 3) encoding of rewards and reward prediction errors in the LP is more robust, necessary, and antecedent to encoding in the VS[6, 7, 9, 14]; 4) LP DBS has been shown to be efficacious in treating disorders with impulse control and compulsive behaviors (e.g., Tourette's, Lesch-Nyhan syndrome) [39, 60-68]; 5) LP DBS has been shown to be safe[39].

2.2 Rationale

Alcohol use disorder (AUD) remains a major cause of mortality, morbidity, and economic burden in the US, accounting for nearly 95,000 annual alcohol-related deaths (5% of US deaths) and estimated costs of \$250 billion/year[75, 76]. Deaths result from liver disease, cardiovascular disease, cancers, and accidents[75, 77-80]. Severe AUD, meeting 6 or more AUD criteria in the DSM-V, makes up about 14% of all AUD patients and accounts for most of the healthcare and economic burden of AUD[81-83]. In this population, chronic excessive alcohol consumption (over 40g/day) invariably leads to alcoholic fatty liver disease. This can progress to liver fibrosis and eventually liver cirrhosis. While mild fibrosis (stages 0-2) is not associated with increased mortality, advanced fibrosis (stages 3-4) is associated with a 10-year mortality rate of 45% and 93% in compensated (asymptomatic) and decompensated (symptomatic) alcoholic liver disease (ALD) patients, respectively. Crucially, nearly 15% of patients with AUD will develop stage 4 liver fibrosis (cirrhosis), which itself carries a 5-year mortality rate of 45%, and accounts for about 23,000 deaths each year, and one-third of total liver transplants in the US[84-86].

Abstinence from alcohol is highly effective in improving outcomes of patients with ALD, raising the 5-year survival rate from 45% to 87%[84, 85, 87, 88]. Across all clinical stages of ALD, abstinence reverses histological features and improves clinical outcome. However, current pharmacologic and behavioral treatments of AUD have limited efficacy in achieving sustained abstinence[83]. Despite increased

knowledge of the neurobiology and circuitry of AUD, the relapse rate to alcohol use has not improved over the past 50 years and the 1-year relapse rate remains at nearly 55% in primary AUD and 90% in AUD among polysubstance use[89]. Thus, identifying novel and more efficacious treatments to maintain abstinence and prevent relapse to alcohol is an urgent public health priority. We propose to test a novel treatment approach for refractory AUD: neuromodulation of the reward circuit with DBS of the limbic pallidum.

As referenced above (section 2.1), the limbic pallidum commands a central role in reward circuitry, both in assigning positive or negative value to stimuli, and in integrating these cues to enhance adaptive behaviors to encountered stimuli. These adaptive behaviors are dysfunctional in SUD, where individuals will compulsively seek drugs despite major adverse outcomes, which is reflected in maladaptive changes to reward circuitry, including the LP. Previous studies, in both animal models and patients (discussed above), demonstrate the efficacy of LP neuromodulation in breaking the circuit of maladaptive processing and arresting drug seeking and relapse to drugs, including alcohol. In addition, LP DBS used for the treatment of disorders of impulsivity (non-SUD) demonstrate its ability to reduce compulsive and impulsive behaviors, which are a hallmark of drug addiction. With the intention of addressing a major cause of mortality and public health and economic burden, the overall objective of this proposal is to conduct an open label pilot study to demonstrate the safety and feasibility of LP DBS in patients with severe AUD and advanced ALD.

3 Hypotheses, Objectives and Endpoints

3.1 Hypotheses

- 3.1.1 Primary Hypothesis: *DBS of the LP in subjects with severe AUD and advanced ALD is safe, tolerable, and feasible.***
- 3.1.2 Secondary Hypothesis: *DBS of the LP in subjects with severe AUD and advanced ALD reduces alcohol use and improves overall functioning.***

3.2 Objectives

- 3.2.1 Primary Objective: *To demonstrate the safety, tolerability, and feasibility of LP DBS for the treatment of severe AUD.***
- 3.2.2 Secondary Objective: *To demonstrate preliminary efficacy of LP DBS to treat severe AUD.***
- 3.2.3 Exploratory Objectives: *To assess the effects of LP DBS on cue reactivity, reward processing, and impulsivity.***

3.3 Endpoints

Primary endpoints: safety, tolerability, and feasibility

Safety and tolerability will be evaluated based on adverse events associated with DBS implantation and stimulation (e.g., infection, bleeding, cognitive or behavioral side effects). We will screen for adverse events using 4 approaches: **1)** patient self-report, **2)** clinical evaluations (medical, neurologic, and psychiatric), **3)** questionnaires to screen for depression, anxiety, apathy, and mania, and **4)** neuropsychological evaluation to screen for any LP DBS effects on the various cognitive domains. These will be compared to DBS side effects observed in FDA approved indications like PD.

Feasibility will be evaluated based on **1)** our ability to recruit all 3 patients within the indicated timeframes, **2)** our ability to conduct the necessary evaluations in baseline and follow-up assessments (e.g., alcohol use, PET imaging, cognitive and behavioral tasks) and **3)** patients' adherence to the study protocol and participation in follow-up visits and assessments.

These outcomes will be monitored throughout the entirety of the study (including recruitment, screening procedure, clinical evaluations, DBS implantation, DBS titration, and all other study-related procedures).

Secondary endpoints: alcohol use, overall functioning, and target engagement

Alcohol use: this will be measured by calculating percent days abstinent (PDA), drinks per drinking day (DDD), blood phosphatidylethanol (PEth) and blood gamma-glutamyl transferase (GGT); PDA and DDD are obtained from TimeLine Followback (TLFB) assessment of alcohol use over the past 180 days for baseline evaluation, and over the past 30 days for follow-up evaluations after DBS implantation. PEth and GGT are blood tests obtained at baseline and every month during follow up visits.

Overall functioning and disability: this will be measured using World Health Organization Disability Assessment Schedule 2.0 (WHODAS 2.0) at baseline and during monthly evaluations after DBS implantation.

Target engagement: this will be measured through changes in brain metabolism with [¹⁸F] fluorodeoxyglucose-PET (FDG-PET). Compared to healthy controls, AUD patients show lower cerebral glucose metabolism (CGM, a surrogate of neuronal activity) in multiple brain regions, as measured with FDG-PET, a finding that has been replicated by several groups [90-96]. Lower prefrontal cortex (PFC) CGM in AUD correlates with neuropsychological deficits (e.g., increased impulsivity) and relapse to alcohol[94-96]. Even after prolonged abstinence from alcohol, low CGM persists in several brain areas including the basal ganglia, orbitofrontal and cingulate cortices[96, 97]. Similar findings were reported in other SUDs and metabolic deficits have been associated with increased craving and compulsivity, and reduced self-control and response inhibition, which are all characteristic of SUDs [98, 99]. Successful therapeutic interventions (e.g., mindfulness training, neurofeedback) were shown to normalize the hypoactivity in affected brain circuits and restore inhibitory control across different misused substances[99, 100]. Ventral striatum DBS was recently shown to increase CGM in the PFC in a subject with severe SUD [101].

FDG PET scans will be obtained at baseline, 1 month after DBS surgery while the DBS is still OFF, then at 6 months after the DBS is turned ON.

Other pre-specified: cue reactivity, impulsivity, reward processing

These are all abnormal in AUD and are associated with vulnerability to relapse in AUD patients.

- Cue reactivity (CR) is the sensitized neurobiological and behavioral assessment of conditioned responses to drug-associated cues [102]. This can manifest as activation of reward circuits and drug craving upon drug-cue presentation[103-106]. CR correlates with AUD severity and predicts relapse risk [107-110]. We will measure CR with the Alcohol Cue Reactivity Task pre- and post-DBS using pictorial cues [111]. Pictorial alcohol cues are sensitive to neuroassessments and evoke strong self-report CR[112], particularly when personalized [113], while avoiding the inherent risks of exposing recently abstinent AUD patients to in-vivo alcohol beverages. CR will be measured with the Cue Reactivity Task; outcome measures: craving, positive affect, negative affect, calm, and excitement scores.
- **Impulsivity:** All types of impulsivity are implicated in AUD[70, 72, 114-120].

- Decisional impulsivity: **will be measured with the delay discounting task which** correlates with AUD severity and predicts risk of relapse [120, 121]; **outcome measure:** discounting rate.
- **Motor impulsivity:** will be measured with Stop Signal Reaction Time task (SSRT) [122, 123]. Motor impulsivity and loss of inhibitory control (**measured with SSRT**) are hallmarks of AUD [71, 124-126]; **outcome measure:** SSRT.
- **Reward processing:** will be measured with the Card Guessing Task (CGT); Reward processing is impaired in AUD[127-130]. This dysfunction is associated with abnormal neural activity recorded on EEG; the AUD-associated neurophysiological abnormalities include increased baseline spectral power (in the β - and γ -bands) and reduced event-related spectral power[131-135]. CGT has shown that reward-processing correlates with an increase in event-related spectral power in the β - and γ -bands, measured with EEG over the left ventrolateral PFC (vIPFC) [136]. To study the effects of LP DBS on the neural activity underlying reward processing in AUD, we will record brain activity with EEG while participants complete the CGT pre- and post-DBS[136, 137]; **outcome measure:** baseline and event-related spectral perturbations in the β - (15-30 Hz) and γ -bands (40-80 Hz) over the vIPFC (at electrode F7).
- **Risk taking:** will be measured with the Balloon Analog Risk Task (BART). BART measures risk taking which is predictive of alcohol-related behaviors in AUD patients [138-140]. **Outcome measure:** number of "adjusted pumps", defined as the average number of pumps on balloons, excluding those that burst [140].

4 Research Design

This will be an open-label trial to demonstrate the safety, tolerability and feasibility of LP DBS for treatment of severe AUD. The intervention is bilateral implantation of deep brain stimulation electrodes in the limbic pallidum in a single cohort of three patients. This study will be conducted at a single site (UPMC Presbyterian hospital, University of Pittsburgh). The study intervention will last from DBS implantation to the patients' 12-month follow-up evaluations (see details in section 6). Bias in research design is not a concern due to the open-label safety and feasibility nature of the study.

Since the primary outcomes of this study are safety, tolerability, and feasibility, adverse effects will be assessed on each participant at regular intervals throughout participation.

5 Human Subjects

5.1 Subject Population

The goal is to implant DBS in 3 participants (male and female), 21-75 years old, with severe AUD and advanced liver disease (stage 3 liver fibrosis, or compensated cirrhosis/stage 4 fibrosis), living in Western Pennsylvania. Due to potential screen fails, 3-10 subjects will be enrolled (consented) and screened. We will stop enrolling subjects when 3 participants are implanted with DBS. This study will not include vulnerable populations; only adults (>21) with the capacity and competence to fulfill informed consent will be allowed to participate.

All Participants will be referred to an outpatient addiction clinic to receive standard of care AUD treatment. We will keep track of the treatments received by every participant throughout the study duration.

Inclusion/exclusion criteria were chosen to maximize both patient safety and the benefit-to-risk ratio, given the invasive nature of this study.

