6.1 Device Selection

The hardware for DBS therapy will include the Percept PC Neurostimulator and the SenSight DBS Directional Leads, both from Medtronic (device brochures are provided in Appendix B). The SenSight electrodes will be surgically implanted bilaterally in the limbic pallidum in the brain, and the Percept stimulator will be implanted into the chest wall. The Percept stimulator will deliver electrical stimulation into the limbic pallidum via the SenSight electrodes. Both devices are FDA approved for Parkinson's disease, essential tremor, and epilepsy. They are also approved via Humanitarian Device Exemption in refractory obsessive compulsive disorder, dystonia.

Percept neurostimulator is the only stimulator that allows recording local field potentials from the area of stimulation. SenSight directional leads were specifically chosen because they allow directional stimulation, minimizing off-target stimulation and associated side-effects.

We have obtained a Right of Reference letter from Medtronic and we will obtain an Investigational Device Exemption from the FDA for the present study.

The intervention will last the entirety of the study, from the time of implantation and throughout the follow-up evaluations. Patients will be evaluated at the end of the study to determine whether intervention will continue after the study. Intervention may be cut short in cases of premature explantation (e.g., adverse events or elective study withdrawal – discussed below).

Implantation will be performed in two stages. First, the DBS directional leads will be neurosurgically implanted that is the same as standard of care DBS implantations for Parkinson's disease (except that the target here is the LP), with an inpatient stay of two to three days. To best guide the electrode placement to our area of interest, we will use each patient's structural MRI and white matter tractography in conjunction with volumetric computed tomography (CT) scan. Second, the neurostimulator will be implanted in an outpatient surgical procedure, 7-10 days after lead implantation; patients will be discharged the same day.

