DBS optimization: Three weeks after the neurostimulator is implanted, we will optimize the DBS settings. DBS titration will be based on stimulation parameters used in previous OCD and SUD studies [101, 144-146]. We will start by screening each contact for clinical effect guided by craving scores and side effects such as photopsia (optic tract), tetanic contraction (posterior limb of internal capsule), or behavioral change (anterior limb of internal capsule). While it is unclear if LP DBS results in acute effects on alcohol craving, we will attempt to optimize DBS settings while measuring craving using the ACQ-SF-R questionnaire and Cue Reactivity task (we will monitor for acute changes in craving scores on the ACQ-SF-R and CR scales with the different DBS settings). If no clear clinical effect is observed, we will identify the optimal electrode contact and stimulation parameters using Lead-DBS software [147, 148]: we will 1) reconstruct and localize the electrodes and 2) simulate the VTiA at different contacts as described in our previous study [69]. DBS will be turned ON in a standard monopolar mode at 135 Hz at the primary and other DBS contacts while monitoring for side effects. We will use pulse width 90-150 μ s and intensity 2-6 V, which proved to be the most effective in OCD and SUD DBS studies [101, 144, 145]. We will use symmetric biphasic pulses, shown to be more efficacious in ameliorating PD and tremor symptoms than other configurations [37, 149-151]. Stimulation intensity will be increased in small increments until we observe side effects or a voltage limit of 10V, whichever is lower, which will be considered the ceiling of stimulation. We will then reduce stimulation intensity to 70% of ceiling voltage.

DBS titration will occur over the course of 2 days. After optimization, DBS will be turned ON continuously at the optimized settings. We will continue to titrate the DBS settings during follow-up visits if participants experience delayed AE or continue to crave and relapse.

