11.1 Adverse Events Requiring Discontinuation

Safety Monitoring Boundaries: Every adverse effect (AE) will be evaluated for severity, expectedness and relatedness and reported to the DSMB. The study will be discontinued (pending DSMB review) if any of the following occurs:

- A higher rate or severity of AE that are definitely, probably, or possibly related to LP DBS compared to standard of care DBS, as assessed by the DSMB.
- Any death, suicide attempt, disability, or other serious AE that is definitely, probably, or possibly related to LP DBS.
- Increased alcohol use in one participant compared to baseline ($>2x$ baseline DDD or $<2x$ PDA) that did not improve with adjusting DBS settings, as identified by AUD assessments in 3 consecutive follow-up visits.

If the study team proposes a well-justified and implementable plan on mitigation of such events, then the study could resume if the DSMB, IRB, and FDA agree.

All other serious adverse events and unexpected events will be reported to and discussed with the DSMB prior to continuing protocol enrollment. The occurrence of a serious adverse event will be grounds for unblinding the data for that participant.

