13.5 Data and Safety Monitoring Board

Since the protocol used in this proposal is classified as “Greater than minimal risk”, an independent Data and Safety Monitoring Board (DSMB) will be created to review and oversee this study. The first meeting of the DSMB will take place before initiation of the study to discuss the protocol, approve the study commencement, and establish guidelines to monitor the study. Follow-up meeting frequency will be determined during the first meeting, and an emergency meeting will be called at any time by the Chairperson, should questions of patient safety arise. After initial approval and at periodic intervals (to be determined by the DSMB committee) during the study, the DSMB responsibilities are to:

1. Review the research protocol, informed consent documents, and plans for data and safety monitoring
2. Evaluate the progress of the study, including periodic assessments of data quality and timeliness, participant recruitment, accrual and retention, participant risk versus benefit, adverse events, patient withdrawals, unanticipated problems, performance of the trial site, and other factors that can affect the study outcome
3. Review safety data after the 3 participants have completed 6-months post-DBS assessments, and determine if the study met safety milestones (if the adverse events are not of a higher grade or incidence than expected)
4. Consider factors external to the study when relevant information becomes available, such as scientific or therapeutic developments that may have an impact on the safety of the participants or the ethics of the study
5. Review clinical center performance, make recommendations and assist in the resolution of problems reported by the study team
6. Protect the safety of the study participants
7. Report on the safety and progress of the study
8. Make recommendations to the study team, and if required, to the NIH/NIAAA concerning continuation, termination or other modifications of the study based on the observed beneficial or adverse effects of the study intervention
9. Monitor the confidentiality of the study data and the results of monitoring

10. Assist the study team by commenting on any problems with study conduct, enrollment, sample size and/or data collection
11. Each serious adverse effect will prompt a review by the DSMB, and the study will be suspended until it is determined whether the SAE is study-related or unrelated

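### No interval or DSMB review is required between the three implants, so delayed or stimulation-related harm in the first participant may emerge too late to spare the others brain surgery

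*Protocol*

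**What the plan says.** **Design.** Protocol section 4 places bilateral electrodes "in a single cohort of three patients". Section 5.1 allows 3–10 people to be consented and screened, and ends enrolment as follows: "We will stop enrolling subjects when 3 participants are implanted with DBS". On the novelty of the target, section 2.1 says "no SUD DBS trials have targeted the LP". Section 8.1 adds that intracranial bleeding is likely to be more common in this population than in other DBS patients.

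**Timing.** Section 6.1 has two surgical stages: "the neurostimulator will be implanted in an outpatient surgical procedure, 7-10 days after lead implantation". Programming comes later: "Three weeks after the neurostimulator is implanted, we will optimize the DBS settings". Section 1 summarises this as "Four weeks after DBS system implantation, the DBS system will be turned ON and the stimulation parameters optimized".

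**Safeguards.**
- Section 11.1 discontinues the study, pending DSMB review, on any serious adverse event at least possibly related to the intervention, on a rate or severity of related events above standard DBS, or on raised alcohol use at three consecutive visits.
- Other serious events and unexpected events "will be reported to and discussed with the DSMB prior to continuing protocol enrollment".
- Section 13.5 (item 11) suspends the study on each serious event until relatedness is settled.
- Section 13.5 leaves the frequency of DSMB meetings to the board's first meeting, held before the study starts. The one safety review it ties to a milestone is item 3: "Review safety data after the 3 participants have completed 6-months post-DBS assessments".

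Neither the protocol nor the SAP states a minimum gap between implants, a sentinel participant, or a review that must precede the next operation. Section 12.5 of both documents gives interim analysis as not applicable.

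**The concern.** With three participants, a stopping boundary can prevent an operation only if the information that triggers it arrives before the next operation. Every safeguard in sections 11.1, 11.3 and 13.5 reacts to an event; none makes the next implant wait for the previous participant's data. The item 3 review comes when no planned implant remains to be influenced.

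This matters most for harm that cannot appear early. Section 8.1 lists mania, suicidal ideation, seizures and worse drinking among the risks of titration and stimulation. None of these can be attributed to stimulation before the device is on. Infection and hardware failure can also surface late. What is at stake is an avoidable intracranial operation in the second and third participants.

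**Working it through.** **1. Reproducing the stated interval.** Leads to neurostimulator is 7–10 days, and neurostimulator to programming is three weeks (section 6.1). So 7 + 21 = 28 and 10 + 21 = 31 days from lead surgery to switch-on. This agrees with the four weeks in section 1 when those are counted from lead surgery. If they were counted from the neurostimulator, the interval would be 35–38 days and the gap described here would be wider. I use 28–31.

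**2. Can all three be implanted before the first switch-on?** Two gaps must fit inside 28–31 days, so each can be up to 14–15.5 days. Nothing in the text prevents that. As an example, take participants 2 and 3 implanted 10 and 20 days after participant 1:

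| Participant | Lead surgery (day) | Switch-on (day) |
|---|---|---|
| 1 | 0 | 28–31 |
| 2 | 10 | 38–41 |
| 3 | 20 | 48–51 |

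An event at participant 1's switch-on could still spare participants 2 and 3 stimulation, but not surgery.

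**3. When can the alcohol boundary be met?** Appendix A puts programming on Days 50–51 and visits 9 to 14 on Days 65, 80, 110, 140, 170 and 200. Counting every visit, the third falls on Day 110: 110 − 51 = 59 days after switch-on, or 59 + 28 = 87 to 59 + 31 = 90 days after lead surgery. If only monthly visits count, the third is Day 140 (89 days after switch-on) or Day 170 (119 days), depending on whether Day 80 counts as monthly. These are nominal days, ignoring visit windows.

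**4. When does the milestone review come?** Month 6 is Day 230: 230 − 51 = 179 days after switch-on, so 207–210 days after the third participant's lead surgery at the earliest.

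**5. How likely is the problem?** Section 3.3 refers to recruitment timeframes, but the documents give none, so accrual is an assumption. Suppose gaps between implants are independent and exponential with mean m days. The chance that all three fall within W days of the first is 1 − exp(−W/m)(1 + W/m). The chance that at least one further implant does is 1 − exp(−W/m).

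| Mean gap m (days) | All three within 28 days | At least one more within 28 days | All three within 87 days |
|---|---|---|---|
| 7 | 0.91 | 0.98 | 1.00 |
| 14 | 0.59 | 0.86 | 0.99 |
| 30 | 0.24 | 0.61 | 0.79 |
| 60 | 0.08 | 0.37 | 0.43 |
| 90 | 0.04 | 0.27 | 0.25 |

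For m = 30 and W = 28, W/m = 0.933 and exp(−0.933) = 0.393. Then 1 − 0.393 × 1.933 = 0.24, and 1 − 0.393 = 0.61.

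**6. What do the existing rules cover?**

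| Event in participant 1 | Earliest seen | Does a current rule spare later participants surgery? |
|---|---|---|
| Acute bleed or deficit | Immediate CT (9.1), overnight intensive care (13.4) | Yes, for anyone not yet operated on |
| Late infection or hardware failure | After the acute stay | Only if they are still waiting |
| Stimulation-related serious event | From day 28–31 | Only if they are still waiting |
| Raised alcohol use | About day 87–90 | Only if they are still waiting |
| Unexpected but not serious | Any time | Unclear: the 11.1 hold is on enrolment, which 5.1 equates with consent |

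**The case against.** The case on the other side is substantial, and much of it stands.

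- **Acute surgical harm is already handled.** A bleed seen on the immediate CT stops anyone not yet operated on, even days later. A reader might infer that the boundaries protect no later participant at all; the documents do not support that.
- **Implanted is not the same as stimulated.** Suspension can keep participants 2 and 3 from being switched on. Section 9.1 describes stimulation effects as usually reversible and allows the system to be turned off. What remains is unneeded surgery, which is narrower but real.
- **The target is not wholly new.** Section 2.1 reports pallidal DBS in Tourette's and Lesch-Nyhan syndromes and calls it safe. It says that no *trial* in substance use disorder has used this target; reading that as never tried in addiction goes too far.
- **The DSMB could impose spacing.** It sets monitoring guidelines before the study starts and receives every adverse event. That is true, but nothing obliges it to address the order of implants.
- **Accrual may be slow.** Eligibility is narrow, and with a mean gap of 60 days or more the chance of all three implants within 28 days is 0.08 or less. A second implant in that window is still plausible (0.37 at 60 days), and the 87-day figure stays at 0.43.

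A reader might also put the 16.7% complication rate from section 8.1 into 2p + (1 − p)p and claim that sequencing avoids 0.47 implants. That is not the gain. The formula compares full sequencing with no stopping rule at all, whereas the plan already suspends on serious events, and the rate covers all complications, many of them surgical or not serious. The documents give no rate of delayed or stimulation-related serious events, so the gain cannot be quantified.

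**Conclusion.** The concern holds in a limited form. The text requires neither an interval nor a review between implants, and its own intervals allow all three participants to carry leads before anyone has been stimulated. The exposed window is 28–31 days for any stimulation-related event and about 87–90 days for the alcohol boundary on its earliest reading. Within those windows, delayed or stimulation-related harm in the first participant may come too late to spare the others an implantation. Acute surgical events are largely covered, and participants not yet switched on can still be spared stimulation.

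How likely this is depends on accrual, which is not stated; the probabilities rest on assumed exponential gaps. The figures in protocol sections 1.1 and 7 were not available to me, so the absence of spacing is judged on the text alone. If a figure shows staggering, the text should say so.

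**What to change.** 1. State in protocol sections 4 and 5.1, and among the DSMB duties in 13.5, that implants are sequential: each one after the first follows a documented DSMB review of the previous participant's safety data.
2. Have the sponsor and DSMB set the milestone at the first meeting already planned before study start, including whether, and how much, data with stimulation on are needed. No interval is proposed here.
3. In section 11.1, make the hold for other serious and unexpected events cover implantation as well as enrolment.
4. Give the recruitment timeframe that section 3.3 relies on, allowing for the wait, so that sequencing does not count against feasibility.

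**Cost.** New wording and two short reviews by a board the protocol already provides for. Accrual lengthens by an amount that depends on the milestone. Purely as an illustration, a review at the first visit after switch-on (two weeks later, section 9.1) would mean 28–31 + 14 = 42–45 days per step, or at most 84–90 days over two steps if the next participant were otherwise ready at once. Screening can continue meanwhile. Because screening and baseline span about 4–20 days (section 7.1) and surgery follows baseline by one to two weeks (section 1), someone who waits may need some screening or baseline tests repeated. No extra participants are needed.
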